1.4.2 Part 2 Study Schedule

| Study Timepoint | Screen ⁰ | Pre- Enrollment ⁰ | Enrolment | D1 ¹ | D3 ¹ | D7 | D28 (Wk 4) | D56 (Wk 8) | D84 (Wk 12) | D112 (Wk 16) | D140 (Wk 20) | D168 (Wk 24)* | D1691 | D171 1 | D175 | D196 (Wk 28) | D224 (Wk 32) | D252 (Wk 36) | D280 (Wk 40) | D308 (Wk 44) | D336 (Wk 48) | D364 (Wk 52) | Unscheduled Visit ² |
|--|---------------------|---------------------------------|-----------|-----------------|-----------------|----|------------|------------|-------------|--------------|--------------|---------------|-------|--------|------|--------------|--------------|--------------|--------------|--------------|--------------|--------------|-----------------------------------|
| Window (days) | -56 to -14 | -21 to -14 | - | +1 | ±1 | ±1 | ±7 | ±7 | ±7 | ±7 | ±7 | ±7 | +1 | ±1 | ±1 | ±7 | ±7 | ±7 | ±7 | ±7 | ±7 | ±7 | uled 2 |
| Clinical Procedures/Evaluations | | | | | | | | | | | | | | | | | | | | | | | |
| Study comprehension exam | X | | | | | | | | | | | | | | | | | | | | | | |
| Informed consent | X | | | | | | | | | | | | | | | | | | | | | | |
| Confirmation of identity, age, and residency | | X | | | | | | | | | | | | | | | | | | | | | |
| Physical exam ³ | | X | X | | | X | X | X | X | X | X | X | | | X | X | X | X | X | X | X | X | X |
| Height | | X | | | | | | | | | | | | | | | | | | | | | |
| Weight | | X | X | | | | | | X | | | X | | | | | | X | | | | X | |
| Vital signs (temperature and pulse) | | X | X | | | X | X | X | X | X | X | X | | | X | X | X | X | X | X | X | X | X |
| Medical history ³ | X | X | X | X | X | X | X | X | X | X | X | X | X | X | X | X | X | X | X | X | X | X | X |

⁶ Viral screenings will be performed according to Kenyan MoH guidelines. HIV testing will be 2 rapid diagnostic tests (RDTs), plus DNA PCR if the RDTs are discordant; subject will be referred for medical care for 2 positive RDTs or a positive PCR. Pre- and post-test HIV counseling will be provided.

⁷ EDTA tube will be stored at screening, and hemoglobin typing will be performed; in the rare case that hemoglobin typing detects sickle cell disease, the participant will be considered a late screening failure; sickle cell trait is not an exclusion criterion.

⁸ For PK, 3.5 mL serum will be collected prior to malaria treatment administration.

⁹ Half of the participants will have this blood draw on Day 28 and the other half will have it at Day 84. Accordingly, the total cumulative volume reflects a PK blood volume for Day 28 or Day 84, but not both.

| Study Time | point | Screen ⁰ | Pre- Enrollment ⁰ | Enrolment | D1 1 | D3 ¹ | D7 | D28 (Wk 4) | D56 (Wk 8) | D84 (Wk 12) | D112 (Wk 16) | D140 (Wk 20) | D168 (Wk 24)* | D169 1 | D171 ¹ | D175 | D196 (Wk 28) | D224 (Wk 32) | D252 (Wk 36) | D280 (Wk 40) | D308 (Wk 44) | D336 (Wk 48) | D364 (Wk 52) | Unscheduled Visit ² |
|---|----------|---------------------|---------------------------------|-----------|--------|-----------------|-----|------------|------------|-------------|--------------|--------------|---------------|--------|-------------------|------|--------------|--------------|--------------|--------------|--------------|--------------|--------------|-----------------------------------|
| Window (da | ays) | -56 to -14 | -21 to -14 | - | +1 | ±1 | ±1 | ±7 | ±7 | ±7 | ±7 | ±7 | ±7 | +1 | ±1 | ±1 | ±7 | ±7 | ±7 | ±7 | ±7 | ±7 | ±7 | uled |
| Concomitant medications ³ | | | X | X | X | X | X | X | X | X | X | X | X | X | X | X | X | X | X | X | X | X | X | X |
| Dihydroartemis piperaquine administration | sinin- | | X 4 | | | | | | | | | | | | | | | | | | | | | |
| Randomization | | | | X | | | | | | | | | | | | | | | | | | | | |
| Study agent administration | | | | X 5 | | | | | | | | | X 5 | | | | | | | | | | | |
| Adverse events | \$ | | X | X | X | X | X | X | X | X | X | X | X | X | X | X | X | X | X | X | X | X | X | |
| Labora | tory Ev | aluat | ions | | | | | | | | | | | | | | | | | | | | | |
| Test | Tube | | (Blo | od vo | lume i | n mL) |) | | | | | | | | | | | | | | | | | |
| HIV ⁶ | SST | | 0.2 | | | | | | | | | | | | | | | | | | | | | |
| CBC with differential | EDT A | | 0.1 | 0.1 | | | 0.1 | 0.1 | | | | | 0.1 | | | 0.1 | | | | | | 0.1 | | |
| Hemoglobin type | EDT A | | 0.5 7 | | | | | | | | | | | | | | | | | | | | | |
| ALT, Cr | SST | | 0.2 | 0.2 | | | 0.2 | 0.2 | | | | | 0.2 | | | 0.2 | | | | | | 0.2 | | |
| Blood smear and dried blood spot for Pf RT-PCR | - | | 0.4 | 0.48 | | | 0.4 | 0.4 | 0.4 | 0.4 | 0.4 | 0.4 | 0.4 | | | 0.4 | 0.4 | 0.4 | 0.4 | 0.4 | 0.4 | 0.4 | 0.4 | 0.4 |
| PK studies | SST | | 3.1 9 | | | | | 3.1 | | | | | | | | | 3.1 | | | | | 3.1 | | |

Version 6.0 Date: 2 Apr 2024

| Study Timepoint | | Screen ⁰ | Pre- Enrollment ⁰ | Enrolment | D1 1 | D3 ¹ | D7 | D28 (Wk 4) | D56 (Wk 8) | D84 (Wk 12) | D112 (Wk 16) | D140 (Wk 20) | D168 (Wk 24)* | D169 ¹ | D171 1 | D175 | D196 (Wk 28) | D224 (Wk 32) | D252 (Wk 36) | D280 (Wk 40) | D308 (Wk 44) | D336 (Wk 48) | D364 (Wk 52) | Unscheduled Visit ² |
|------------------------|-------------------|---------------------|---------------------------------|-----------|------|-----------------|-----|------------|------------|-------------|--------------|--------------|---------------|-------------------|--------|------|--------------|--------------|--------------|--------------|--------------|--------------|--------------|-----------------------------------|
| Window (days) | | -56 to -14 | -21 to -14 | - | +1 | ±1 | ±1 | ±7 | ±7 | ±7 | ±7 | ±7 | ±7 | +1 | ±1 | ±1 | ±7 | ±7 | ±7 | ±7 | ±7 | ±7 | ±7 | uled |
| Serum storage | SST | | (X) | | | | | (X) | | | | | | | | | (X) | | | | | (X) | | |
| ADA | SST | | (X) | | | | | (X) | | | | | | | | | (X) | | | | | (X) | | |
| Daily volume | Daily volume (mL) | | 4.5 | 0.7 | - | - | 0.7 | 3.8 | 0.4 | 0.4 | 0.4 | 0.4 | 0.7 | - | - | 0.7 | 3.5 | 0.4 | 0.4 | 0.4 | 0.4 | 3.8 | 0.4 | |
| Cumulative volume (mL) | | - | 4.5 | 5.2 | 5.2 | 5.2 | 5.9 | 9.7 | 10.1 | 10.5 | 10.9 | 11.3 | 12.0 | 12.0 | 12.0 | 12.7 | 16.2 | 16.6 | 17.0 | 17.4 | 17.8 | 21.6 | 22.0 | - |

Abbreviations: ADA, anti-drug antibodies; ALT, alanine transaminase; CBC, complete blood count; Cr, creatinine; D, day; EDTA, ethylenediaminetetraacetic acid; HIV, human immunodeficiency virus; M, month; Pf, *Plasmodium falciparum*; PK, pharmacokinetics; SST, serum-separating tube; RT-PCR, reverse transcription polymerase chain reaction.

(X) indicates that no additional blood will be drawn; the test will be performed from the tube shown in the preceding row.

Footnotes:

⁰ Screening and pre-enrolment visits may be combined. Screening activities may be performed and/or repeated at pre-enrolment visit to ensure they are completed within the allowable window as described in section 8.1 (14 to 21 days prior to D0). As long as physical exam, height and weight measurement, vital signs, medical history, and concomitant medications are done at the pre-enrolment visit, they do not necessarily need to be done at the screening visit, if the two are separate visits.

¹ Home-based visits.

² At any time during the study, the subject may have an unscheduled illness visit if experiencing malaria symptoms or other symptoms. The subject may be referred for standard care according to local guidelines.

³ Complete/comprehensive at screening; targeted/interim at other visits.

⁴ The first dose of dihydroartemisinin-piperaquine will be directly observed in the clinic if possible, but might be given in the participant's home. The subsequent 2 doses given over the following 2 days will be observed by guides in the subject's home or at the clinic. All dihydroartemisinin-piperaquine doses will be completed prior to day 0 and will be initiated between 21 and 14 days prior to D0.

⁵ L9LS or placebo. All other study procedures must be completed prior to study agent administration. Subjects who received L9LS at day 0 will receive L9LS or placebo at month 6; those in the placebo arm will receive a second placebo injection at 6 months. Each subject will be monitored for at least 60 minutes after study agent

administration and vital signs will be recorded 1 hour after study agent administration. Prior to discharge, subject will be assessed for local reactogenicity (including pain/tenderness, swelling, redness, bruising, and pruritus at the site of injection) and systemic reactogenicity (including fever, feeling unusually tired or unwell, muscle aches, headache, chills, nausea, and joint pain). If the subject is assessed as being unwell or has ongoing reactogenicity symptoms, he or she will be asked to remain in the clinic until evaluation and discharge by a study clinician. Clinicians will follow any solicited symptoms that are ongoing until they have resolved.

⁶ Viral screenings will be performed according to international guidelines. HIV testing will be 2 rapid diagnostic tests (RDTs), plus DNA PCR if the RDTs are discordant; subject will be referred for medical care for 2 positive RDTs or a positive PCR. Pre- and post-test HIV counseling will be provided.

⁷ EDTA tube will be stored at screening, and hemoglobin typing will be performed; in the rare case that hemoglobin typing detects sickle cell disease, the participant will be considered a late screening failure; sickle cell trait is not an exclusion criterion.

⁸ Collected prior to study agent administration. Other indicated tests may be performed after study agent administration.

⁹ For PK, 3.5 mL serum will be collected prior to malaria treatment administration.

^{*} The timing of all visits subsequent to Day 168 (administration of dose 2) will be in relation to the Day 168 visit, whenever that occurs; for example, if the Day 168 visit occurs on Day 161, the first day of the window, the Days 169 and 171 home visits will occur 1 and 3 days later (so on days 162 and 164 in relation to dose 1).

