| Serum storage | SST | | (X) | | | | (X) | | | (X) | | (X) | |
| ADA | SST | | (X) | | | | (X) | | | (X) | | (X) | |
| Daily volume (mL) | - | 4.5 | 0.4 | - | - | 3.8 | 0.7 | 0.4 | 3.8 | 0.4 | 3.8 9 | | |
| Cumulative volume (mL) | | - | 4.5 | 4.9 | 4.9 | 4.9 | 8.7 | 9.4 | 9.8 | 13.6 | 14.0 | 14.7 9 | - |

Abbreviations: ADA, anti-drug antibodies; ALT, alanine transaminase; CBC, complete blood count; Cr, creatinine; D, day; EDTA, ethylenediaminetetraacetic acid; ELISA, enzyme-linked immunosorbent assay; HIV, human immunodeficiency virus; M, month; Pf, Plasmodium falciparum; PK, pharmacokinetics; SST, serum separating tube; RT-PCR, reverse transcription polymerase chain reaction.

(X) indicates that no additional blood will be drawn; the test will be performed from the tube shown in the preceding row.

Footnotes:

⁰ Screening and pre-enrolment visits may be combined. Screening activities may be performed and/or repeated at pre-enrolment visit to ensure they are completed within the allowable window as described in section 8.1 (14 to 21 days prior to D0). As long as physical exam, height and weight measurement, vital signs, medical history, and concomitant medications are done at the pre-enrolment visit, they do not necessarily need to be done at the screening visit, if the two are separate visits.

¹ Days 1 and 3 will be home visits, with a phone call assessment if child is not able to be seen after 2 attempts.

² At any time during the study, the subject may have an unscheduled illness visit if experiencing malaria symptoms or other symptoms. The subject may be referred for standard care according to Kenya Ministry of Health treatment guidelines.

³ Complete/comprehensive at screening; targeted/interim at other visits.

⁴ The first dose of dihydroartemisinin-piperaquine will be directly observed in the clinic if possible, but might be given in the participant's home. The subsequent 2 doses given over the following 2 days will be observed by study staff in the subject's home or at the clinic. All dihydroartemisinin-piperaquine doses will be completed prior to day 0 and will be initiated between 21 and 14 days prior to D0.

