1.4.4 Part 2 Extension Study Schedule

| Study Timepoint | Consent for Extension Phase ⁰ | Pre-Enrolment | Enrolment (D0) | Y2D1 ¹ | Y2D3 ¹ | Y2D7 | Y2D28 (Wk 4) | Y2D56 (Wk 8) | Y2D84 (Wk 12) | Y2D112 (Wk 16) | Y2D140 (Wk 20) | Y2D168 (Wk 24)* | Y2D169 ¹ | Y2D171 ¹ | Y2D175 | Y2D196 (Wk 28) | Y2D224 (Wk 32) | Y2D252 (Wk 36) | Y2D280 (Wk 40) | Y2D308 (Wk 44) | Y2D336 (Wk 48) | Y2D364 (Wk 52) | Unscheduled Visit ² |
|--|--|---------------|----------------|-------------------|-------------------|------|--------------|--------------|---------------|----------------|----------------|--------------------|---------------------|---------------------|--------|----------------|----------------|----------------|----------------|----------------|----------------|----------------|-----------------------------------|
| Window (days) | Before Parasit Clearance ⁰ | -21 to -14 | - | +1 | ±1 | ±1 | ±7 | ±7 | ±7 | ±7 | ±7 | ±7 | +1 | ±1 | ±1 | ±7 | ±7 | ±7 | ±7 | ±7 | ±7 | ±7 | luled 1-2 |
| Clinical Proced | ures/E | valuat | ions | | | | | | | | | | | | | | | | | | | | |
| Study comprehension exam | X | | | | | | | | | | | | | | | | | | | | | | |
| Informed consent | X | | | | | | | | | | | | | | | | | | | | | | |
| Confirmation of identity, age, and residency | X | | | | | | | | | | | | | | | | | | | | | | |
| Physical exam | | X | X | | | X | X | X | X | X | X | X | | | X | X | X | X | X | X | X | X | X |
| Height | | X | | | | | | | | | | | | | | | | | | | | | |
| Weight | | X | X | | | | | | X | | | X | | | | | | X | | | | X | |
| Vital signs (temperature, pulse) | | X | X | | | X | X | X | X | X | X | X | | | X | X | X | X | X | X | X | X | X |
| Medical history | X | X | X | X | X | X | X | X | X | X | X | X | X | X | X | X | X | X | X | X | X | X | X |
| Concomitant medications | | X | X | X | X | X | X | X | X | X | X | X | X | X | X | X | X | X | X | X | X | X | X |
| Dihydroartemisinin- piperaquine administration | | X 4 | | | | | | | | | | | | | | | | | | | | | |
| Randomization | | | X | | | | | | | | | | | | | | | | | | | | |

| Study Time | point | Consent for Extension Phase ⁰ | Pre-Enrolment | Enrolment (D0) | Y2D1 ¹ | Y2D3 ¹ | Y2D7 | Y2D28 (Wk 4) | Y2D56 (Wk 8) | Y2D84 (Wk 12) | Y2D112 (Wk 16) | Y2D140 (Wk 20) | Y2D168 (Wk 24)* | Y2D169 ¹ | Y2D171 ¹ | Y2D175 | Y2D196 (Wk 28) | Y2D224 (Wk 32) | Y2D252 (Wk 36) | Y2D280 (Wk 40) | Y2D308 (Wk 44) | Y2D336 (Wk 48) | Y2D364 (Wk 52) | Unscheduled Visit ² |

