
Risks of MAb Administration: Administration of MAbs may cause immune reactions such as acute anaphylaxis, serum sickness, and the generation of antibodies. However, these reactions are rare and more often associated with MAbs targeted to human proteins or with the use of

mouse MAbs that would have a risk of human anti-mouse antibodies.²⁶ In this regard, because L9LS is targeted to a parasite antigen and is a human MAb, it is expected to have a low risk of such side effects.

Typically, the side effects of MAbs are mild to moderate and may include local reactions at the injection site (including pain, redness, bruising, swelling, pruritis) and systemic reactions such as fever, chills, rigors, nausea, vomiting, pain, headache, myalgia, arthralgia, dizziness, fatigue, shortness of breath, bronchospasm, hypotension, hypertension, pruritus, rash, urticaria, angioedema, diarrhea, tachycardia, or chest pain. Healthcare staff will be appropriately trained and necessary medical equipment will be readily available at the clinic where the study agent is administered. Clinical use of MAbs that are targeted to cytokines or antigens associated with human cells may be associated with an increased risk of infections; ²⁶ however, this is not expected to be a risk for a MAb targeted to a parasite antigen.

Severe reactions, such as anaphylaxis, angioedema, bronchospasm, hypotension, and hypoxia, are infrequent and more often associated with MAbs targeted to human proteins or with non-human MAbs, such as a mouse MAb.²⁶ Most administration-related events occur within the first 24 hours after MAb administration.

Published experience with human MAbs directed against cell surface targets on lymphocytes shows that administration of a MAb may be associated with cytokine release, causing a reaction known as cytokine release syndrome (CRS).²⁷ CRS reactions commonly occur within the first few hours of administration and with the first MAb administration received. This is because the cytokine release is associated with lysis of the cells targeted by the MAb and the burden of target cells is greatest at the time of the first MAb treatment. With licensed therapeutic MAbs, CRS is managed by administering histamine blockers.²⁸ Supportive treatment may also be indicated for some signs and symptoms.

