8.3 Safety and Other Assessments

The following study procedures and evaluations will be done according to the schedule in section 0 to monitor safety and support the understanding of the study intervention's safety. The assessment and collection of safety events such as AEs are described in section 8.4.2.

Physical Examination: As described in section 8.2.1, physical examination will also be performed for assessment of safety.

Vital Signs: Vital signs (temperature and heart rate) will be collected at visits, including before and after study agent injection, as described in section 8.2.1.

Safety Blood Laboratory Evaluations: The following safety laboratory evaluations will be performed at a frequency presented in section 0:

- CBC with differential.
- ALT, Cr.

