8.4.2.1.1 Severity Grading

The investigator will grade the severity of fever (by non-oral temperature reading) and each blood laboratory testing AE according to the "Adverse Event Grading Scale" (see Appendix B).

Events that are not gradable using the "Adverse Event Grading Scale" (e.g. seizures) will be graded according to the Common Toxicity Criteria for Cancer Research table version 2.0 (https://ctep.cancer.gov/protocoldevelopment/electronic_applications/docs/ctcv20_4-30-992.pdf)

Events that are NOT gradable using either of the above specified tables will be graded as follows:

- Mild = grade 1
- Moderate = grade 2
- Severe = grade 3
- Potentially life threatening = grade 4
- Death = grade 5

NOTE: A subject death should always be reported as grade 5.

8.4.2.1.1.1 Laboratory Value Assessment and Clinical Significance Criteria

ALL abnormal lab values of grade 3 or above are REPORTABLE as AE or SAE (if applicable, i.e. if the child needs admission or other SAE criteria are fulfilled).

Grade 1 and 2 abnormal laboratory values will be considered CLINICALLY SIGNIFICANT, and will be recorded in the research database, and reported, ONLY if they meet ONE or more of the following criteria:

- result in a study agent dosage adjustment, interruption, or discontinuation
- are accompanied by clinically abnormal signs or symptoms that are likely related to the laboratory abnormality (e.g., clinical jaundice)
- indicate a possible organ toxicity (e.g., elevated serum creatinine [Cr])
- result in additional/repeat testing or medical intervention (procedures/treatments) (e.g., electrolytes have to be repeated after potassium supplementation for hypokalemia)
- are considered clinically significant by the investigator or SMM

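### No temperature is scheduled between discharge on dosing day and the Day 7 visit, so early fever, part of the 7-day primary safety endpoint, may be under-counted and poorly graded

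*Combined protocol and SAP*

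**What the plan says.** Section 3 defines the primary safety endpoint by both incidence and severity over the 7 days after dosing, plus SAEs throughout. Fever heads the list of systemic reactogenicity items in the schedule footnotes and in section 6.1.2.4. Section 8.4.2.1.1 ties its grade to a measurement: "The investigator will grade the severity of fever (by non-oral temperature reading". Appendix B gives the cut-offs in °C.

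The schedules place the readings. Section 1.4.2 has "Vital signs (temperature and pulse) | | X | X | | | X | X" and section 1.4.4 has "Vital signs (temperature, pulse) | | X | X | | | X | X". In both rows the marks fall at pre-enrolment, D0 and D7, with D1 and D3 empty. Physical examination is empty there too; only history, concomitant medications and adverse events are marked. Sections 1.4.1 and 1.4.3 show the same pattern. In part 2 the D1 and D3 contacts are "Home-based visits". In parts 1 and 1b they are home visits, "with a phone call assessment if child is not able to be seen after 2 attempts".

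Section 8.3 says "Vital signs (temperature and heart rate) will be collected at visits, including before and after study agent injection", but its opening sentence defers to the schedule and the sentence goes on to cite section 8.2.1, which sets no D1 or D3 reading. Section 2.3.1 notes: "Most administration-related events occur within the first 24 hours after MAb administration".

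**The concern.** Staff are with the child at home on D1 and D3, inside the period when reactions to the product are most expected, yet no temperature is marked. A fever that starts after discharge and settles before D7 leaves no scheduled reading behind it. What remains is the carer's account, which can say that the child felt hot but cannot place the episode in an Appendix B band.

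The youngest children (eligible from 5 months) cannot report headache, nausea or aches, so fever carries more of the systemic assessment in them. The day-7 data also decide whether part 1b moves from the 30 mg/kg to the 40 mg/kg group and whether the extension goes ahead (section 4.1.1). Safety at 20–40 mg/kg is the first primary objective of the extension. Missed fevers make all of these look cleaner than they are.

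**Working it through.** **1. Are the blanks real?** Each vital-signs row was split into cells and matched to its column headers, to rule out a shift from PDF extraction.

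| Schedule | Cells / columns | Vital signs not marked at |
|---|---|---|
| 1.4.1 and 1.4.3 (parts 1, 1b) | 12 / 12 | Screening, D1, D3 |
| 1.4.2 (part 2) | 23 / 23 | Screening, D1, D3, D169, D171 |
| 1.4.4 (extension) | 23 / 23 | Consent visit, Y2D1, Y2D3, Y2D169, Y2D171 |

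The blanks are real and recur after each dose.

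**2. How long is the gap?** It starts at the vital signs about 1 hour after dosing. Section 6.1.2.4 makes it later for some children: observation lasts at least 4 hours (first two per arm) or 2 hours (the rest) in part 1, and 2 hours for the first two per dose group in part 1b, with vital signs before discharge. It ends at D7, which is day 6–8 in part 2 and the extension (±1) and day 5–9 in parts 1 and 1b (±2). A part 2 child has 8 post-dose assessments inside the two 7-day windows (D0 after dosing, D1, D3, D7, and the same four from D168). Four of the 8 have no temperature. Between discharge and D7, it is both contacts of 2 after each dose.

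**3. Can history supply the grade?** In Appendix B, grades 1 and 2 are 37.5–37.9 and 38.0–38.4 in parts 1 and 1b (each 0.4 °C wide), and 37.5–38.4 and 38.5–39.4 in part 2 and the extension (each 0.9 °C wide). Recall without a reading cannot choose between them.

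**4. Does another rule close the gap?** The rule in section 4.1 that brings febrile children to clinic belongs to contacts made 2 weeks after scheduled visits, starting after the first monthly visit. Around dose 2 these fall nominally at D154 (140 + 14) and D182 (168 + 14), outside D168–D175. Vital signs are marked for unscheduled visits, but those depend on the carer coming. No diary or home thermometer is described.

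**5. What would equal under-capture do?** Let s be the fraction of true events captured, the same in all arms, with no false positives. The observed risk is s × p, so the observed difference is s × (p₂ − p₁). The documents give no value of s; those below are assumptions. The tables used concern adverse events in general and serve only to show scale.

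*Between arms.* Section 9.3, Table 7, first row: 108 per arm, 0.05 against 0.169. Two-sided test at 0.05, normal approximation with pooled variance under the null: power = Φ{[d − 1.96·√(2p̄(1−p̄)/n)] / √[(p₁(1−p₁) + p₂(1−p₂))/n]}. At s = 1 this gives 80.4%, reproducing the plan's 80%.

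*Within a part 1b dose group.* Pr(no event) = (1 − s × 0.2)⁹ for 9 recipients at a true rate of 0.2. All four values appear in Table 5.

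| s | Observed rates | Difference | Power, n = 108 | Rate s × 0.2 | Pr(0 of 9) |
|---|---|---|---|---|---|
| 1 | 0.050 vs 0.169 | 0.119 | 80% | 0.20 | 0.134 |
| 0.75 | 0.0375 vs 0.127 | 0.089 | 67% | 0.15 | 0.232 |
| 0.50 | 0.025 vs 0.0845 | 0.0595 | 48% | 0.10 | 0.387 |
| 0.25 | 0.0125 vs 0.042 | 0.030 | 27% | 0.05 | 0.63 |

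**The case against.** The best defence is that the plan has other routes to a reading. Section 8.4.2 has adverse events elicited at each contact by questioning and examination. Sick visits are open at any time, have vital signs marked and are partly reimbursed. Section 8.4.2.1.1 also has a fallback mild-to-severe scale for events its tables cannot grade. This stands as far as it goes. A reader might infer that early fever cannot be measured or graded at all; the documents do not support that. They do leave the reading to initiative, because examinations are not marked at these contacts.

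Other stronger readings also fail:

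- **The text contradicts the table.** This is weak: section 8.3 defers to the schedule. The wording should be aligned, but it is not a plain conflict.
- **A missed grade 3 fever would defeat the pausing rule.** Section 8.4.5 needs two events of grade 3 or higher in one subject, unexpected and at least possibly related. One fever cannot trigger it.
- **The arms would be biased against each other.** Assessors are blinded and contacts are the same in all arms, so no differential bias is evident. The effect is dilution, which still favours a finding of no difference.
- **The rat study signals fever.** The rise was at most 0.5 °C and was judged non-adverse (section 2.2.1.2.2), so it adds little. The 24-hour remark in section 2.3.1 closes a paragraph on severe reactions, and should not be pressed as a statement about fever alone.

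Timing limits what can still change. Version 6.0 is dated 2 April 2024. Part 1 is reported as done (section 2.3.1). Part 2 visits were due to end by June 2024 (section 1.1), so the last D171 contact fell about 193 days (364 − 171) earlier, near the end of 2023.

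**Conclusion.** The point holds in this form: no temperature is scheduled between discharge on dosing day and D7, after any dose in any part. Early fever may therefore be under-counted and poorly graded, similarly in all arms. The schedule gap is certain, because the cells align in all four tables. How much fever is lost is unknown and may be small if home-visit staff carry thermometers or carers come in readily. The power and probability figures show direction and scale under assumed capture rates, not an estimate. The practical consequence is largest for part 1b, where groups of 9 recipients and a day-7 review decide what follows, and for the extension, where safety is a primary objective. This is a cheap improvement to make, not a flaw that invalidates the safety analysis.

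**What to change.** - In section 1.4.3, mark a non-oral temperature and an injection-site check at D1 and D3. In section 1.4.4, mark them at Y2D1, Y2D3, Y2D169 and Y2D171.
- Align sections 8.3 and 8.4.2 with the schedule, so that the text says which contacts include a reading.
- Where only a phone call takes place, record temperature as not measured, never as no fever.
- Keep the subject-level analysis of section 9.5.5. Tabulate fevers known only from history separately as ungraded, and state by arm how many subjects had a reading. Do not switch the denominator to contacts.
- For parts 1 and 2, where dosing is probably complete, state the gap as a limitation when fever rates and grades are reported.

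The cost is a thermometer for home-visit staff, one CRF field and a schedule edit. No visit or blood draw is added.
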